#### DS107 Cream Medicinal Ingredients:

DGLA (Di-hommo-gamma-linolenic acid)

#### DS107 Cream Non-Medicinal Ingredients:

**Table 4: DS107 Cream Non-Medicinal Ingredients**

Excipient	Function	Status
Steareth-2	Primary Emulsifier	Ph.Eur
Steareth-21	Primary Emulsifier	Manufacturer's In-house Specification
Cetyl Alcohol	Co-emulsifier	Ph.Eur
L(+)Ascorbyl Palmitate	Anti-oxidant	Ph.Eur
all-rac- $\alpha$ -Tocopherol	Anti-oxidant	Ph.Eur
Medium Chain Triglycerides	Emollient	Ph.Eur
Myristyl Myristate	Co-emulsifier, Emollient	Manufacturer's In-House Specification
Isopropyl Palmitate	Emollient	Ph.Eur
Glycerol, Anhydrous	Humectant	Ph.Eur
Methyl 4-Hydroxybenoate	Preservative	Ph.Eur
Ethyl 4-Hydroxybenzoate	Preservative	Ph.Eur
Propyl 4-Hydroxybenzoate	Preservative	Ph.Eur
Bronopol	Preservative	Manufacturer's In-House Specification
Ascorbic Acid	Antioxidant	Ph.Eur
Carbomer	Viscosity Modifier	NF
Xanthan Gum	Thickener	Ph.Eur
Soy Lecithin	Stabilizing Agent	Manufacturer's In-house Specification
Potassium Hydroxide	pH adjustment	Ph.Eur
Mild Care 345	Fragrance	Manufacturer's In-house Specification

Water For Irrigation	Solvent	Ph.Eur
----------------------	---------	--------

**Vehicle cream:**

A matching vehicle cream is also supplied. This is identical in composition to the DS107 cream formulation minus active drug substance. The vehicle formulation is based on the formulation of the investigational medicinal product with additional water for irrigation being used to compensate for the absence of active pharmaceutical ingredient in the formulation.

**Vehicle Cream Medicinal Ingredients:**

None

**Vehicle Cream Non-Medicinal Ingredients:****Table 5: Vehicle Non-Medicinal Ingredients**

Excipient	Function	Status
Steareth-2	Primary Emulsifier	Ph.Eur
Steareth-21	Primary Emulsifier	Manufacturer's In-house Specification
Cetyl Alcohol	Co-emulsifier	Ph.Eur
L(+)Ascorbyl Palmitate	Anti-oxidant	Ph.Eur
all-rac- $\alpha$ -Tocopherol	Anti-oxidant	Ph.Eur
Medium Chain Triglycerides	Emollient	Ph.Eur
Myristyl Myristate	Co-emulsifier, Emollient	Manufacturer's In-House Specification
Isopropyl Palmitate	Emollient	Ph.Eur
Glycerol, Anhydrous	Humectant	Ph.Eur
Methyl 4-Hydroxybenzoate	Preservative	Ph.Eur
Ethyl 4-Hydroxybenzoate	Preservative	Ph.Eur
Propyl 4-Hydroxybenzoate	Preservative	Ph.Eur
Bronopol	Preservative	Manufacturer's In-House Specification
Ascorbic Acid	Antioxidant	Ph.Eur
Carbomer	Viscosity Modifier	NF
Xanthan Gum	Thickener	Ph.Eur
Soy Lecithin	Stabilizing Agent	Manufacturer's In-house Specification
Potassium Hydroxide	pH adjustment	Ph.Eur
Mild Care 345	Fragrance	Manufacturer's In-house Specification
Water For Irrigation	Solvent	Ph.Eur

Drug bulk product and vehicle are manufactured by C.P.M. ContractPharma GmbH & Co., Germany and packaged by Anderson Brecon Limited, UK. Labelled DS107 cream and

---

matching vehicle cream will be supplied by Anderson Brecon Limited to a central distribution facility as a cream formulation in aluminium tubes packed in cartons with tamper evident seals.

IMPs will be stored at ambient condition (i.e. up to 25°C) and should be used within the assigned expiry date.

## 10.2 Supply, Packaging, Labelling, Handling and Storage

DS107 cream and vehicle cream will be provided by the Sponsor.

The DS107 cream and vehicle cream will be a white to off white-cream formulation supplied from the manufacturer to the central distribution facility. The central distribution facility will supply the IMP and vehicle to site where it will be handled by the site pharmacy or responsible personnel according to local Regulations. Patients who qualify for randomisation at Baseline/Visit 2 will be given IMP for 2 weeks/14 days at Baseline/Visit 2, Week 2/Visit 3, Week 4/Visit 4, and Week 6/Visit 5.

The DS107 cream and vehicle cream will be labelled with information according to local regulation.

The study medication will be provided by the Sponsor to the Investigator and will be kept, on site, in a locked room or cabinet with limited access. The DS107 cream and vehicle cream will be stored at a controlled room temperature of ambient condition (ie. Up to 25°C) in a secure area protected from unintended use and will only be supplied to patients in the trial under the supervision of the Investigator.

## 10.3 Dosage and Administration

IMP at dose strengths of 5% and 1% DS107 cream or vehicle cream will be topically applied liberally to all affected or commonly affected areas twice daily (morning and evening) by the patients. **The last study drug application should occur on the day preceding Week 8 (Visit 6) /early termination (ET) visit.** Patients will be randomized to one of the three treatment groups in a 1:1:1 ratio:

- Treatment group A: 1% DS107 cream applied topically to all affected or commonly affected areas twice-daily for 8 weeks

- Treatment group B: 5% DS107 cream applied topically to all affected or commonly affected areas twice-daily for 8 weeks
- Treatment group C: Vehicle cream applied topically to all affected or commonly affected areas twice-daily for 8 weeks

An area for treatment will be defined at study start and DS107 or vehicle cream will be applied to all that area (and any newly affected areas) for the complete 8 week duration. Emollients can be applied to other areas of dry skin not in the defined treatment area.

DS107 or vehicle cream will not be applied on the morning of clinic visits 3, 4, 5, and 6 (will be applied as soon as all of the efficacy assessments are complete during the clinic visit). To maintain the blind throughout the study, the DS107 cream and vehicle cream will be identical in appearance.

If a patient misses one application of the study product they should apply the study product as usual at the time of the next scheduled application. Patients should remember to note the missed application in the Patient Compliance Log.

#### **10.4 Duration of Treatment**

Patients will topically apply either DS107 cream or vehicle cream liberally to all affected or commonly affected areas twice daily for 8 consecutive weeks.

#### **10.5 Methods for Assigning Patients to Treatments**

Approximately 300 patients will be randomized into double-blind treatment groups in a 1:1:1 ratio by an Interactive Web Response System (IWRS) as follows:

- Treatment group A: 1% DS107 cream applied topically to all affected or commonly affected areas twice-daily for 8 weeks
- Treatment group B: 5% DS107 cream applied topically to all affected or commonly affected areas twice-daily for 8 weeks
- Treatment group C: Vehicle cream applied topically to all affected or commonly affected areas twice-daily for 8 weeks

---

A randomization list, permuted blocks and stratified by site will be generated by DS Biopharma or its designee. The randomization schedule with study drug assignments will be generated prior to the start of the study and will be known only to the individuals responsible for labelling the study drug, the statisticians generating the schedule and the IWRS team responsible for implementing the schedule. The IWRS will assign a medication kit number to each patient and the contents will be based on the randomization code.

At the investigational site, each patient will be assigned a patient identifier number during screening that will be used on all patient documentation. The patient identifier number will contain the site number and the patient number assigned in numerical order at the screening visit (e.g.: 102-10 for the tenth patient screened at the site number 02). Patient numbers will be assigned in ascending order starting with 01.

## 10.6 Drug Accountability

All IMP supplied for this study must be retained in a safe place at all times of the study. Only personnel authorised by the principal Investigator at each site should dispense the IMP and the accountability is the responsibility of the Investigator. The Investigator or pharmacist must complete the IMP supply form, verifying the receipt of IMP. The patients should return all used and unused tubes of IMP to the study site at every visit. Following compliance assessment the tubes of IMP will be retained in a secure location at the site until the end of the study. After the Clinical Research Associate (CRA) has completed a final drug accountability review the IMP will be returned or destroyed only when instructed by the CRA.

## 11 ADVERSE EVENTS AND SERIOUS ADVERSE EVENTS

### 11.1 Definitions of Adverse Events

#### 11.1.1 Seriousness

##### *Adverse Events (AE):*

Any undesirable experience occurring to a patient who has signed the ICF and has taken their first dose of the study drug, whether or not considered related to the investigational IMP(s). All AEs must be recorded in the case report form, defining relationship to IMP and severity. AEs should also be recorded by the Investigator in the patients file/notes.

##### *Serious Adverse Events (SAE):*

If a patient experiences a serious adverse event after the first dose of the study drug, the event will be recorded as a SAE.

*A SAE (experience) or reaction is any untoward medical occurrence that at any dose:*

- results in death
- is life-threatening
- requires in-patient hospitalization or prolongation of existing hospitalization
- results in persistent or significant disability/incapacity, or
- is a congenital anomaly/birth defect

Note: The term "life-threatening" in the definition of "serious" refers to an event in which the patient was at risk of death at the time of the event. It does not refer to an event which hypothetically might have caused death if it were more severe.

Medical and scientific judgment should be exercised in deciding whether expedited reporting is appropriate in other situations, such as important medical events that may not be immediately life-threatening or result in death or hospitalization but may jeopardize the patient or may require intervention to prevent one of the other outcomes listed in the definition above. These should also usually be considered serious.

Examples of such events are intensive treatment in an emergency room or at home for allergic bronchospasm, blood dyscrasias or convulsions that do not result in hospitalization, or development of drug dependency or drug abuse.

##### *Unexpected Adverse Event (UAE):*

---

An experience not previously reported in the Investigator's Brochure or similar product information sheet such as the Summary of Products Characteristics (SPC).

### 11.1.2 Severity

The intensity of an AE is an estimate of the relative severity of the event made by the Investigator based on his or her clinical experience. The following definitions are to be used to rate the severity of an AE:

- Mild: The adverse event is transient and easily tolerated.
- Moderate: The adverse event causes the patient discomfort and interrupts the patient's usual activities.
- Severe: The adverse event causes considerable interference with the patient's usual activities, and may be incapacitating or life-threatening.

### 11.1.3 Relationship to IMP

The Investigator will establish causality of the AE to experimental treatment. The Investigator should take into account the patient's history, most recent physical examination findings, and concomitant medications.

The following definitions will be used to determine causality of an AE:

- Not related: temporal relationship of the onset of the AE, relative to the experimental treatment is not reasonable or another cause can explain the occurrence of the AE.
- Related: temporal relationship of the onset of the AE, relative to the experimental treatment is reasonable, follows a known response pattern to the treatment, and an alternative cause is unlikely.

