## **11.2 Serious Adverse Reactions and Unexpected Adverse Reactions**

### **11.2.1 Definitions**

#### ***Adverse Reaction:***

All noxious and unintended responses to a medicinal product related to any dose should be considered adverse drug reactions.

The phrase "responses to a medicinal product" means that a causal relationship between a medicinal product and an AE is at least a reasonable possibility i.e. the relationship cannot be ruled out.

For marketed medicinal products, an adverse reaction is a response to a drug which is noxious and unintended and which occurs at doses normally used in man for prophylaxis, diagnosis, or therapy of disease or for modification of physiological function.

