#### ***Unexpected Adverse Reaction:***

---

An adverse reaction, the nature or severity of which is not consistent with the applicable product information (e.g. Investigator's Brochure for an unauthorised investigational product or similar product information sheet such as the Summary of Products Characteristics (SPC)).

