***Suspected Unexpected Serious Adverse Reaction (SUSAR):***

Any serious adverse reaction that might be related to the IMP and is unexpected according to the definition above.

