### 12.9.3 Safety variables

The type and frequency of AEs will be summarised by MedDRA system organ class and preferred term per treatment group. In addition, the number and proportion of patients with at least one adverse event will be summarised per treatment group.

The number and proportion of patients experiencing SAEs, AEs leading to withdrawal and AEs possibly or probably related to treatment will be summarized per treatment group.

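### Protocol 11.1.3 and 11.2.1 set contradictory causality thresholds, which leaves some events without a valid rating and may under-count drug-related events

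*Protocol*

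**What the plan says.** Protocol 11.1.3 gives the rating to the investigator: "The Investigator will establish causality of the AE to experimental treatment". It offers two categories.

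- *Related* joins three conditions: the timing is reasonable, and the event "follows a known response pattern to the treatment, and an alternative cause is unlikely".
- *Not related* needs only one of two: the timing "is not reasonable or another cause can explain the occurrence of the AE".

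Protocol 11.2.1 uses a different standard. For an adverse reaction, the causal link has to be "at least a reasonable possibility i.e. the relationship cannot be ruled out". An unexpected reaction is one "the nature or severity of which is not consistent with the applicable product information". A SUSAR is defined as "Any serious adverse reaction that might be related to the IMP and is unexpected according to the definition above".

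Protocol 11.1.4 requires a relationship to IMP in the case report form for every AE. It also requires each potential SAE to be notified to the PV CRO within 24 hours, with the investigator's preliminary view of causality. Protocol 11.2.2 makes the PV CRO responsible for reporting SUSARs.

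On analysis, Protocol 12.8 tabulates AEs by relationship among other factors, and 12.9.3 states that "AEs possibly or probably related to treatment will be summarized per treatment group". SAP 2.2.13.3 counts subjects with an IMP-related AE and with an IMP-related SAE, so it treats relatedness as yes or no.

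**The concern.** The investigator's definition of *Related* is much stricter than the protocol's own definition of a reaction. An event of a kind not seen before has no known response pattern, so it cannot meet the strict definition, yet such events are among those a SUSAR process exists to find. The second limb of *Not related* also allows any sufficient alternative explanation to settle the rating, even when the drug remains a possible cause.

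This second problem matters in this trial. Protocol 1.5 reports erythema, red spots and dry flaky skin at application sites in minipigs. Protocol 1.1 describes atopic dermatitis (AD) as dry, itchy, inflamed skin, and the IGA in Appendix 3 is graded partly on erythema. The disease under study is therefore an available other cause for AD-like signs at the application site. Prior exposure to the cream is put at 294 people (Protocol 1.6), so the stock of known response patterns is limited.

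At stake are the causality view sent with each SAE and the summaries of related AEs and related SAEs. The safety comparison with vehicle is a stated objective.

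**Working it through.** No arithmetic applies. The check is to take four kinds of event through both sets of definitions. Case A assumes that an event of a new kind has no known response pattern; the documents do not define that term.

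| Event | Rating under 11.1.3 | Status under 11.2.1 |
|---|---|---|
| A. New kind, reasonable timing, no other cause | Not *Related* (no known pattern); not *Not related* (timing reasonable, no other cause). No category. | Adverse reaction; a SUSAR if serious and unexpected |
| B. Reasonable timing, another cause can explain it, drug cannot be ruled out | *Not related*, because the "or another cause can explain the occurrence of the AE" limb is enough | Adverse reaction |
| C. Known pattern, unexpected severity, reasonable timing, alternative unlikely | *Related* | Adverse reaction; a SUSAR if serious |
| D. Timing not reasonable, drug ruled out | *Not related* | Not a reaction |

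C and D are consistent. A and B are not: A has no permitted entry although 11.1.4 demands one, and B receives opposite answers.

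Next, where the rating goes.

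1. **Serious events.** Notification under 11.1.4 depends on seriousness, not on causality, so A and B both reach the PV CRO. Section 11.2.1 does not make SUSAR status depend on the label from 11.1.3. However, the causality view that travels with the notification is the investigator's. Neither document says that the PV CRO makes its own assessment or may override that view. SAP 2.2.7 plans no safety monitoring committee.
2. **Non-serious events.** The 24-hour route does not cover these. The investigator's label goes straight into the tables.
3. **Outputs that use the label.** The relationship breakdown in Protocol 12.8, the related-AE summary in 12.9.3, and the related-AE and related-SAE counts in SAP 2.2.13.3.
4. **Outputs that do not.** In SAP 2.2.13.3, the counts of any AE, any SAE and discontinuations due to an AE, and the treatment-emergent AEs by system organ class and preferred term.

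Last, the categories. Protocol 12.9.3 names two positive grades. Protocol 11.1.3 collects one, and the SAP uses one, so the 12.9.3 summary cannot be produced as worded.

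**The case against.** The strongest reply is that the safety system does not rest on the label in 11.1.3. A reader might infer that the SUSAR pathway cannot work or that new kinds of serious reaction are not escalated. The documents do not support this: every potential SAE goes to the PV CRO within 24 hours, section 11.2.1 carries its own lower threshold, and 11.1.4 asks for notice after the study of any AE potentially related to the IMP. Nor can one infer that almost no unexpected reaction could be rated *Related*. Unexpectedness covers severity as well as nature (case C), and a known response pattern is not equated with listing in the product information.

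A reader might also infer that the whole comparison with vehicle is biased. That fails too. An under-attributed event is still counted among all treatment-emergent AEs, and ratings are made by blinded staff (Protocol 12.4) under one definition in every arm.

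On application-site signs, it can fairly be said that erythema and flaking, once described, are a known pattern, that the finding comes from minipigs, and that 11.1.3 tells investigators to weigh history and examination findings. This weakens any claim that all such signs would be rated *Not related*. It does not remove the risk, because an available other cause is sufficient for *Not related* even when the pattern is known.

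These replies limit the consequences. They leave the gap in case A and the contradiction in case B untouched, and the 24-hour rule does nothing for non-serious events.

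**Conclusion.** The concern holds as a contradiction within the protocol. Followed literally, 11.1.3 gives no valid entry for a new kind of event with plausible timing and no other cause. It also rates as *Not related* some events that 11.2.1 calls adverse reactions. SUSAR identification may be steered wrongly by the investigator's preliminary view, and the related-AE and related-SAE summaries may under-count drug-related events, including application-site signs that resemble AD.

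The size cannot be given: the documents contain no expected rate of related events. The exposure is limited to outputs that use the causality rating; tables of all treatment-emergent AEs stand. The conclusion assumes that investigators apply the definitions as written, and that the PV CRO does not reassess causality, a point on which the documents are silent. This should be fixed, but it does not undermine the safety evaluation as a whole.

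**What to change.** Reconcile 11.1.3, 11.2.1 and 12.9.3 around the threshold the protocol already has.

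- In 11.1.3, define *Related* as a causal relationship being at least a reasonable possibility, and *Not related* as no reasonable possibility.
- Remove the known-pattern requirement. Another possible cause may be weighed, but should no longer be sufficient on its own for *Not related*.
- In 12.9.3, replace the two grades with the single category *related*, matching the two-level scale and SAP 2.2.13.3.

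A sentence on whether the PV CRO makes its own causality assessment would settle the point left open above.

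The cost is protocol wording and CRF completion guidance, with no new data or visits. The downside is that more AEs will be rated related, in all arms, by an amount the documents do not allow one to estimate. Because every patient has AD, this may make the related-AE table somewhat less discriminating.

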### 11.1.4 Reporting of AEs and SAEs

All AEs must be recorded in the case report form, defining relationship to IMP and severity.

The frequency of each AE should always be recorded to indicate if the event is intermittent, continuous, a one time event, etc. If the same AE occurs repeatedly at approximately the same strength in the same patient, this AE should be counted only once. If any aspect of the AE changes (including but not limited to severity, frequency, causality) a new AE should be recorded. AE start and end dates should be clearly defined in the CRF.

---

**As soon as the Investigator is aware of a potential SAE, he/she should contact the pharmacovigilance (PV) CRO monitor by phone, fax or e-mail, and in any case no later than 24 hours after the knowledge of such a case. The contact information, is provided in the Investigator Site File.**

At the time of the call, the Investigator must provide as a minimum requirement, the patient number, birth date, nature of the SAE, and a preliminary assessment of causality. The Investigator should follow-up the initial notification of the potential SAE by faxing a copy of the SAE reporting form to the PV CRO at the number provided in the Investigator Site File. The faxed SAE reporting form should be received to the PV CRO within 24 hours after knowledge of such a case.

Follow-up information on an existing SAE that is fatal or life-threatening should be reported by the Investigator to the PV CRO within 5 days after the initial report. Where appropriate, hospitalisation or autopsy reports should be made available. All SAEs will be followed up until resolution (i.e., asymptomatic, stabilisation or death).

AEs should be reported for the entire study duration up to and including the follow up period. Following completion of the study, if the Investigator becomes aware of any AE that is potentially related to the IMP the Sponsor should be notified.

## **11.2 Serious Adverse Reactions and Unexpected Adverse Reactions**

### **11.2.1 Definitions**

#### ***Adverse Reaction:***

All noxious and unintended responses to a medicinal product related to any dose should be considered adverse drug reactions.

The phrase "responses to a medicinal product" means that a causal relationship between a medicinal product and an AE is at least a reasonable possibility i.e. the relationship cannot be ruled out.

For marketed medicinal products, an adverse reaction is a response to a drug which is noxious and unintended and which occurs at doses normally used in man for prophylaxis, diagnosis, or therapy of disease or for modification of physiological function.

